1. INTRODUCTION

The purpose of this reporting and analysis plan (RAP) is to describe the streamlined analyses to be included in the synoptic Clinical Study Report and/or regulatory disclosure for Protocol GSK205744:

Revision Chronology:		
Version 01	15-Jul-2016	Original
Amendment 1	08-MAY-2017	Addition of language to include a stopping rule that halts enrollment upon the occurrence of any encephalopathy, unless clearly attributable to central nervous system disease involvement or inter-current illness. Minor clarifications, correction of typographical errors, reformatting of tables, administrative and grammatical changes to text and Time and Events tables/footnotes.

Given the premature termination of the study, the study objectives and the statistical analyses planned (or described) in the protocol are no longer appropriate. Consequently, the reporting and analysis plan will be abbreviated to the tables and listings described in this document.

A streamlined final reporting will be conducted after all required database cleaning activities have been completed and final database release and database freeze has been declared by Data Management.

This is an open label study so there will be no special criteria for unblinding.

2. SUMMARY OF KEY PROTOCOL INFORMATION - STUDY OBJECTIVE(S) AND ENDPOINT(S)

2.1.1. Part 1: Dose Confirmation and Escalation

Objectives	Endpoints
Primary Objectives	Primary Endpoints

 To determine the recommended phase 2 dose (RP2D) of GSK2879552 administered alone and in combination with Azacitidine in adult subjects with HR MDS previously treated with HMA. 	
 AEs, SAEs, dose limiting toxicities, dose reductions or delays, withdrawals due to toxicities and changes in safety parameters (e.g., laboratory values, vital signs, electrocardiograms [ECGs], physical examinations).
Secondary Objectives	Secondary Endpoints

 To evaluate clinical activity after treatment with GSK2879552, alone or in combination with 	
 Clinical benefit rate (CBR) defined as % of subjects achieving CR, mCR, PR, HI or SD. Objective response rate (ORR)

Objectives	Endpoints
Azacitidine, in adult subjects with HR MDS previously treated with HMA.	defined as % of subjects achieving CR, mCR, PR, or HI [as per 2006 IWG criteria].

 To measure the exposure to GSK2879552 alone and to GSK2879552 and Azacitidine in combination, in patients with HR MDS previously treated with HMA. 	
 GSK2879552 and Azacitidine concentrations pre-dose and post-dose.

 To evaluate duration of response, duration of clinical benefit, progression-free survival and overall survival. 	
 Duration of response (DOR) defined as the time from first documented response to disease progression. Progression-free survival (PFS) defined as the time from first dosing day to disease progression or death from any cause. Overall survival (OS) defined as the time from first dosing day until death from and cause.

 To evaluate frequency and time to progression to AML (per 2006 IWG criteria). 	
 Proportion of subjects with disease progression to AML. Time to AML progression.

 To evaluate platelet and RBC transfusion dependence. 	
 Number of documented platelet and RBC transfusions per month prior to study entry and on study.
Exploratory Objectives	Exploratory Endpoints

 To investigate the mechanism of action and indicators of sensitivity and resistance to GSK2879552 alone and in combination with Azacitidine. 	
 Gene and/or protein expression studies of peripheral blood and/or bone marrow aspirates; correlation of baseline epigenetic and genomic profiles with response.

2.1.2. Part 2: Expansion Cohorts (This part of the study was not initiated)

Objectives	Endpoints
Primary Objectives	Primary Endpoints

 To evaluate clinical activity after treatment with GSK2879552, alone or in combination with Azacitidine, in adult subjects with HR MDS previously treated with HMA. 	
 Clinical benefit rate (CBR) defined as % of subjects achieving CR, mCR, PR, HI or SD. Objective response rate (ORR) defined as % of subjects achieving CR, mCR, PR, or HI [as per 2006 IWG criteria].
Secondary Objectives	Secondary Endpoints

 To further evaluate the safety and tolerability of GSK2879552 	
 Changes in safety parameters: e.g. AEs and SAEs, changes in laboratory values,

Objectives	Endpoints
administered alone or in combination with Azacitidine.	vital signs, electrocardiograms [ECGs], and physical examinations.

 To characterize the population PK of GSK2879552, alone or in combination with Azacitidine in patients with HR MDS previously treated with HMA. To evaluate duration of response, duration of clinical benefit, progression-free survival, and overall survival. 	
 Population PK parameters for GSK2879552 such as clearance (CL/F). Duration of response (DOR) defined as the time from first documented response to disease progression. Progression free survival (PFS) defined as the time from first dosing day to disease progression or death from any cause. Overall survival (OS) defined as the time from first dosing day until death from any cause.

 To evaluate frequency and time to progression to AML (per 2006 IWG criteria) To evaluate platelet and RBC transfusion dependence. 	
 Proportion of subjects with disease progression to AML. Time to AML progression. Number of documented platelet and RBC transfusions per month within 3 months prior to study entry and while on study.
Exploratory Objectives	Exploratory Endpoints

 To investigate the mechanism of action and indicators of sensitivity and resistance to GSK2879552 administered alone or in combination with Azacitidine to patients with HR MDS previously treated with HMA. To evaluate the relationship of exposure of GSK2879552, administered alone or in combination with Azacitidine, and safety/efficacy parameters, based on Part 1 and 2 data combined. To investigate the relationship between genetic variants in host DNA and the safety, tolerability, and efficacy of GSK2879552 alone or in combination with azacitidine based on Part 1 and 2 data combined. 	
 Gene and/or protein expression studies of peripheral blood and/or bone marrow aspirates; correlation of baseline epigenetic and genomic profiles with response. Relationship between GSK2879552 exposure markers (e.g. dose, concentration, Cmax or AUC (0-tau)) and safety/clinical activity. Pharmacogenomic (PGx) analysis using saliva samples.

3. PLANNED REPORTING

Only Part 1 of the study was initiated so the scope of the planned reporting will be limited to Part 1. Summaries for primary and secondary endpoints for Part 1 will be reported. Other relevant Part 1 data will be listed. There are no data to report for Part 2.

4. ANALYSIS POPULATIONS

Population	Definition / Criteria	Analyses Evaluated
All Treated Subjects Population	
 This will consist of all subjects who received at least one dose of study treatment. Safety and clinical activity data will be evaluated based on this population. 	
 Study Population Safety Clinical Activity
Pharmacokinetic Population	
 This population will consist of all subjects in the All Treated Subject Population for whom a blood sample for pharmacokinetics is obtained and analysed. 	
 Pharmacokinetic analysis

5. CONSIDERATIONS FOR REPORTING

The reporting will be based on the All Treated Subjects population, unless otherwise specified. All summaries will be presented by treatment group initially treated and overall unless otherwise specified. All subjects in the study belong to one treatment group so all summaries will display only one group.

5.1. Study Population Reporting

Patient disposition, demographic characteristics and race will be summarized using IDSL standard reporting shells as indicated in Section 5.7.1.

5.2. Efficacy Reporting

Secondary efficacy (clinical activity) endpoints will be summarized using IDSL standard reporting shells as indicated in Section 5.7.2. The following are considerations for handling and/or reporting secondary efficacy endpoints:

Clinical benefit rate and objective response rate in monotherapy group will be displayed using the All Treated Subjects Population and based on the disease assessment data up to crossover and prior to new anti-cancer therapy.

For the time to event efficacy endpoints (including DOR, PFS and Time to AML), crossover will be considered as censor situation (if no progressions before crossover) using the All Treated Subjects Population. The number of subjects with progression to AML will apply the same AML definition as the one used in time to event endpoint.

OS is defined as the time from first treatment dose until death due to any reason regardless of crossover using the All Treated Subjects Population.

Platelet and RBC transfusions will apply the same rule as CBR and ORR to present summaries by treatment group using the All Treated Subjects Population.

Objective response rate and Clinical benefit rate

This study employs response criteria from IWG criteria [Cheson, 2006] for response definition. The Clinical Benefit Rate (CBR) is defined as the percentage of subjects achieving a confirmed Complete Remission (CR) or Partial Remission (PR) or Marrow Complete Remission (mCR) or confirmed Hematologic Improvement (HI) or Stable Disease (SD) prior to new anti-cancer therapy and crossover on the All Treated Subjects Population.

Objective response rate is defined as the percentage of subjects who achieved CR or PR or mCR or HI prior to new anti-cancer therapy on the All Treated Subjects Population.

Subjects with Not Evaluable or missing response will be treated as non-responders; i.e. they will be included in the denominator when calculating the percentage.

The CBR and ORR will be reported for combined treatment group in Part 1 with the same drug and the same dose. Confirmed and unconfirmed response summaries will be provided. The number and types of responses, as outlined in IWG criteria [Cheson, 2006, also presented in the table below], will be produced, along with two-sided 95% exact confidence interval (CI).

The CBR and ORR differences between the two cohorts will be provided along with corresponding two-sided 95% exact confidence interval (CI). A chi-square test will be used to test for differences between arms if the data warrant. Otherwise, a fisher's exact test will be employed if sample sizes are small at the beginning of trial.

IWG CRITERIA FOR RESPONSE

Category	Response Criteria
Complete Remission	
Bone marrow: $\leq 5\%$ myeloblasts with normal maturation of all cell lines^a
 
Persistent dysplasia will be noted^{a,b}
 
Peripheral blood (Response must be maintained for at least 4 weeks)
 
Hgb ≥ 11 g/dL
 
Platelets ≥ 100 Gi/L
 
Neutrophils ≥ 1.0 Gi/Lb
 
Blasts 0%

Partial Remission	All CR criteria if abnormal before treatment except: Bone marrow blasts decreased by $\geq 50\%$ over pre-treatment but still $>$

	5% Cellularity and morphology not relevant
Marrow CRb	Bone marrow: $\leq 5\%$ myeloblasts and decrease by $\geq 50\%$ over pretreatments Peripheral blood: if HI responses, they will be noted in addition to marrow CRb
HI	Erythroid (HI-E): hgb increase of > 1.5 g/dL decrease of $>$ RBC transfusions/8weeks versus pretreatment requirement in previous 8 weeks; only RBC transfusions given for a pretreatment Hgb of < 9.0 g/dL count Platelet (HI-P): increase of $> 30,000/\text{mL}$ (starting with $> 20,000/\text{mL}$) increase from $< 20,000/\text{mL}$ to $> 20,000/\text{mL}$ by $> 100\%$ Neutrophil (HI-N): increase of $> 100\%$ and $> 500/\mu\text{L}$
Stable Disease	Failure to achieve at least PR, but no evidence of progression > 8 wks
Disease Progression	For subjects with:  Less than 5% BM blasts: $\geq 50\%$ increase in blasts to $> 5\%$ blasts  5%-<10% BM blasts: $\geq 50\%$ increase to $> 10\%$ blasts  10%-<20% BM blasts: $\geq 50\%$ increase to $> 20\%$ blasts  20%-30% BM blasts: $\geq 50\%$ increase to $> 30\%$ blasts Any of the following:  At least 50% decrement from maximum remission/response in granulocytes or platelets  Reduction in Hgb by $\square 2$ g/dL  Transfusion dependence
Non-evaluable	Subject does not meet any of the above criteria

BM = bone marrow ; CR = complete remission; Hgb = hemoglobin;; PR = partial remission

a. Dysplastic changes should consider the normal range of dysplastic changes (modification).

b. Modification to IWG response criteria [[Cheson](#), 2006].

Progression-free Survival

Progression-free survival (PFS) is defined as the time from first treatment dose until the first documented sign of disease progression or death. For the analysis of Progression-free survival (PFS), if the subject received subsequent anti-cancer therapy or crossed over from monotherapy to combination therapy prior to the date of documented events, PFS will be censored at the last adequate assessment prior to the initiation of anti-cancer therapy and crossover. If the subject missed more than one visit prior to the date of documented events, PFS will be censored at the last adequate assessment prior to missing. Otherwise, if the subject does not have a documented date of events, PFS will be

censored at the date of the last adequate assessment. The description of PFS could be summarized as Table 1 using the All Treated Subjects Population.

Table 1 Progression-free Survival

Situation	Date of Progression or Censoring	Outcome
No baseline disease assessments	Date of first dose	Censored
No post-baseline disease assessments	Date of first dose	Censored
Crossover before progression	Date of disease assessment prior to crossover	Censored
Progression documented between scheduled visits	Date of disease assessment	Progressed
No progression	Last date of disease assessment	Censored
New anticancer treatment started	Date of disease assessment prior to initiation of anti-cancer therapy	Censored
Death before first PD assessment	Date of death	Progressed
Death between adequate assessment visits	Date of death	Progressed
Death or progression after more than one missed visit	Date of disease assessment prior to missed visits	Censored

Duration of Response

Duration of response is defined as the subset of subjects (responders) who show a response (CR, mCR, PR, or HI), the time from first documented evidence of response until the first documented sign of disease progression or death. If no disease progression or death, the DOR will be censored at last disease assessment. The same censoring and event rules for PFS will be applied for DOR using the All Treated Subjects Population.

Overall Survival

Overall survival (OS) is defined as the time from first treatment dose until death due to any reason. For the analysis of overall survival (OS), the last date of known contact will be used for those subjects who have not died at the time of analysis; such subjects will be considered censored.

AML Progression

The proportion of subjects with disease progression to Acute Myeloblastic Leukemia (AML) is defined as the percentage of patients experiencing AML on the All Treated Subjects Population. The number of patients experiencing progression due to AML will be summarized using the All Treated Subjects Population as well. Time to AML progression is defined as the time from first treatment dose until AML progression or crossover if using the All Treated Subjects Population. For the analysis of time to AML,

if the subject did not experience AML, time to AML will be censored at the last treatment prior to the initiation of anti-cancer therapy or crossover.

Documented Platelet and RBC Transfusions

The number and percentage of documented platelet and RBC transfusions per month prior to study entry and during the treatment period will be produced on the All Treated Subjects Population. The number of transfusions will be summarized on the data up to crossover for monotherapy treatment on the All Treated Subjects Population.

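### Do the differing confirmation and crossover qualifiers in the ORR and CBR definitions allow ORR to exceed CBR, or leave the reported endpoint undefined?

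*SAP*

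**What the plan says.** Section 2.1.1 gives the Part 1 secondary endpoints without reference to confirmation: "Clinical benefit rate (CBR) defined as % of subjects achieving CR, mCR, PR, HI or SD", and ORR "defined as % of subjects achieving CR, mCR, PR, or HI [as per 2006 IWG criteria". CBR is thus the ORR set with SD added.

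Section 5.2 opens with a rule naming both rates in the monotherapy group: they are "based on the disease assessment data up to crossover and prior to new anti-cancer therapy". Under its subheading on the two rates it then defines each formally:

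- The response part of the CBR sentence reads "percentage of subjects achieving a confirmed Complete Remission (CR) or Partial Remission (PR) or Marrow Complete Remission (mCR) or confirmed Hematologic Improvement (HI". Its closing part, which adds the remaining category and sets the data cut, reads "Stable Disease (SD) prior to new anti-cancer therapy and crossover on the All Treated Subjects Population".
- ORR is given by "Objective response rate is defined as the percentage of subjects who achieved CR or PR or mCR or HI prior to new anti-cancer therapy".

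The same subsection adds "Subjects with Not Evaluable or missing response will be treated as non-responders" and "Confirmed and unconfirmed response summaries will be provided".

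Section 5.7.2 lists Table 2.1 (best response without confirmation) and Table 2.2 (with confirmation). The programming note for Table 2.1, which Table 2.2 adopts, puts ORR and CBR in one table without a p-value. Both tables have the same delivery priority and are marked for FDAAA and EudraCT.

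**The concern.** CBR should contain every ORR responder, because it is the same list of categories with SD added. The formal sentences do not preserve this. CBR carries a confirmation requirement for CR and HI and a crossover cut; the ORR sentence mentions neither. A reader who programs from those sentences alone could obtain an ORR larger than the CBR, which the endpoint table in Section 2.1.1 rules out.

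The SAP also plans confirmed and unconfirmed versions of both rates, four figures for two endpoints, and does not name a lead version. The study stopped early (Section 1), so some responses may never have been confirmed, and the two versions may differ. If one could be chosen after the data were seen, the disclosed result would depend on that choice.

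**Working it through.** No sample size, power or event figure is involved. The check is whether the ORR responders are always contained in the CBR set, first under the definition sentences and then under the planned outputs.

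**Step 1: denominator.** Both rates use the All Treated Subjects Population, and non-evaluable or missing responses stay in the denominator. ORR can exceed CBR only if its numerator does.

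**Step 2: crossover.** The ORR sentence omits crossover, but the opening rule of Section 5.2 applies the cut to both rates in the monotherapy group. The PFS text in the same section describes crossover only from monotherapy to combination, so the rule covers everyone who could cross over. A first response after crossover therefore counts in neither rate. The omission is a slip.

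**Step 3: confirmation, from the sentences alone.** No general rule covers confirmation, so the mismatch is real at this level. It is narrow, however:

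- An unconfirmed HI without progression for more than 8 weeks can enter CBR as SD.
- An unconfirmed CR may qualify as marrow CR, which carries no confirmation qualifier of its own in the CBR sentence.
- The IWG table already requires the peripheral blood part of CR to be maintained for at least 4 weeks.

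The secure example is an unconfirmed HI, with no marrow response, followed by progression within 8 weeks.

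**Step 4: confirmation, in the planned tables.** Each title fixes one confirmation basis for the whole table. The note defines CBR as the ORR categories plus SD; it adds cytogenetic response, but to both rates. All responses below occur before new therapy, and the first two before any crossover.

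| Subject | Sentences alone | Table 2.1 | Table 2.2 |
|---|---|---|---|
| Unconfirmed HI, progression within 8 weeks | ORR yes, CBR no | ORR yes, CBR yes | ORR no, CBR no |
| Unconfirmed HI, no progression for more than 8 weeks | ORR yes, CBR yes (as SD) | ORR yes, CBR yes | ORR no, CBR yes (as SD) |
| First response after crossover, no SD before it | ORR yes, CBR no | ORR no, CBR no | ORR no, CBR no |

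In neither table is there a subject with ORR yes and CBR no. This follows from the construction: adding SD to a set cannot make it smaller.

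**Step 5: which version is the endpoint result.** The planned figures are 2 tables × 2 rates = 4. The ORR sentence is silent on confirmation; it does not call for unconfirmed responses, and no sentence assigns a rate to a table. Pairing an unconfirmed ORR with a confirmed CBR is an inference, and no planned table makes that pairing. Section 5.2 announces both versions, so an unconfirmed CBR in Table 2.1 is a declared second presentation.

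**The case for a change.** The strongest case for a change is that the confirmation mismatch is real, that no general rule repairs it as one does for crossover, and that the repair is cheap: two edited sentences and a programming note. Four rates for two endpoints with no lead version is untidy, particularly where early termination may leave responses unconfirmed. The uncertainty also reaches duration of response (Table 2.4), whose responder set is defined in Section 5.2 without confirmation status.

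Much of this stands as a description of the drafting. The two sentences should have matched, and naming a lead table would be good practice. It does not show a wrong or selectively reported result. Both tables are produced at the same priority, both are marked for disclosure, and each is labelled by confirmation status, so nobody has to choose one after seeing the data. A statement that confirmation applies to neither rate in Table 2.1 and to both in Table 2.2 would largely repeat the titles. For duration of response, the responder set is a detail the analyst must settle and can footnote. Listing 27 shows each subject's response with and without confirmation, and Listing 28 shows the durations, so either reading can be recovered.

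**Conclusion.** The uneven wording is a clerical slip and no change to the plan is needed. On the definition sentences alone, ORR can count a subject whom CBR omits; in the planned outputs it cannot. Followed as written, the SAP yields two labelled, internally consistent descriptive tables. The effect of aligning the sentences on ORR and CBR in Tables 2.1 and 2.2 is nil.

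Little rests on these rates beyond description. They are secondary Part 1 endpoints in a streamlined report after early termination, the tables carry no p-value, Section 5 states that all subjects belong to one treatment group, and no decision is shown to depend on them.

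This assumes that programmers apply each table's stated confirmation basis to both of its rates and use the crossover rule that opens Section 5.2. Both are the natural reading. The SAP gives neither the number treated nor the number of unconfirmed responses, so the gap between the confirmed and unconfirmed rates cannot be estimated, but both will be visible to the reader.

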5.7.2. Efficacy Tables: Clinical Activity

Efficacy: Tables					
No.	Population	IDSL / Example Shell	Title	Programming Notes	Deliverable [Priority]
Efficacy Tables: Clinical Activity					
2.1.	All treated	RE1a	Summary of Investigator-Assessed Best Response (Without Confirmation) (IMWG 2016)	
FDAAA, EudraCT Notes: Summarize by arm; Do not include Total. Best Response: Complete response (CR), molecular Complete Remission (mCR), Partial Response (PR), Cytogenetic Response, Hematologic Improvement (HI), or Stable Disease (SD), Not Evaluable (NE). Add a category of 'Missing' if summarize for Unconfirmed response. Objective Response Rate (ORR): % of subjects achieving CR, mCR, PR, Cytogenic Response, or HI. Clinical Benefit Rate (CBR): % subjects achieving CR, mCR, PR, Cytogenic Response, HI, or SD. Include: ORR and CBR (No p-value) in one table.
	SAC [1]

Efficacy: Tables					
No.	Population	IDSL / Example Shell	Title	Programming Notes	Deliverable [Priority]
2.2.	All treated	RE1a	Summary of Investigator-Assessed Best Response (With Confirmation) (IMWG 2016)	FDAAA, EudraCT Note: See comments above for table 2.1.	SAC [1]
2.3.	All treated	TTE1	Summary of Progression-free Survival	FDAAA, EudraCT	SAC [1]
2.4.	All treated	TTE1a	Summary of Duration of Response	FDAAA, EudraCT	SAC [1]
2.5.	All treated	TTE1	Summary of Overall Survival	FDAAA, EudraCT	SAC [1]
2.6.	All treated	TTE1a	Summary of Time to AML	FDAAA, EudraCT	SAC [1]
2.7.	All treated	BPA1	Summary of Documented Platelet Transfusions	FDAAA, EudraCT	SAC [1]
2.8.	All treated	BPA1	Summary of Documented RBC Transfusions	FDAAA, EudraCT	SAC [1]

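### Do the two-cohort comparison of response rates and the unclear grouping by dose need correcting in a study with one treatment group?

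*SAP*

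**What the plan says.** Four places in the SAP bear on how ORR and CBR are grouped and compared.

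- **Section 5 (Considerations for Reporting)** gives a default and then a fact. The default is "All summaries will be presented by treatment group initially treated and overall unless otherwise specified". The fact is "All subjects in the study belong to one treatment group so all summaries will display only one group".
- **Section 5.2, on the rates themselves:** "The CBR and ORR will be reported for combined treatment group in Part 1 with the same drug and the same dose". Each is to carry a two-sided 95% exact confidence interval.
- **Section 5.2, on comparison:** "The CBR and ORR differences between the two cohorts will be provided along with corresponding two-sided 95% exact confidence interval (CI". Next comes "A chi-square test will be used to test for differences between arms if the data warrant", with Fisher's exact test as the fallback for small samples.
- **Section 5.7.2, programming notes to Table 2.1**, which Table 2.2 adopts by reference: "Summarize by arm; Do not include Total" and "Include: ORR and CBR (No p-value) in one table".

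Two further places give context. Section 1 says that, because the study ended early, the analyses planned in the protocol no longer fit and reporting is cut down to the displays this document lists. Section 2.1.1 titles Part 1 as dose confirmation and escalation, and Section 3 confirms that only Part 1 was started.

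**The concern.** The comparison sentence is unconditional. It commits the team to a difference with an interval, while Section 5 says there is only one group. A plan that promises something it cannot deliver invites a deviation note, or leads someone to create a second group in order to satisfy it.

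The grouping looks loose as well. Sharing drug and dose suggests one rate per dose level. Treatment group initially treated suggests regimen, because the crossover described under Progression-free Survival is for subjects who "crossed over from monotherapy to combination therapy". One regimen in an escalation part could cover several doses. The table note speaks of arms and drops the total, whereas the Section 5 default adds an overall column. If these instructions really pointed in different directions, the denominators and exact intervals for ORR and CBR would be settled at programming rather than in the plan.

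**Working it through.** The SAP gives no number treated, number of doses used or number of responders, so it has no figure to reproduce. The check is mainly a comparison of text, with illustrative arithmetic under stated assumptions.

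**1. Can the comparison be computed?** With one group, the second group has n₂ = 0. The difference x₁/n₁ − x₂/n₂ contains 0/0 and is not estimable. Take an assumed 1 responder in 6 against an empty second row. The expected counts in that row are 0 × 1/6 = 0 and 0 × 5/6 = 0, so the chi-square statistic is undefined. Fisher's test has only one table compatible with the margins, so it returns p = 1.0 and an undefined odds ratio. The promise cannot be met.

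**2. Is the comparison scheduled anywhere?** Section 5.7.2 lists eight tables: best response without and with confirmation (2.1, 2.2), progression-free survival (2.3), duration of response (2.4), overall survival (2.5), time to AML (2.6), and platelet and RBC transfusions (2.7, 2.8). None is assigned a difference or a test, and the Table 2.1 note rules out a p-value. Section 1 confines reporting to the listed displays. The deliverables therefore resolve the contradiction in favour of Section 5, and deleting the sentences would change no output.

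**3. Does the Table 2.1 note conflict with Section 5?** The overall column is a default that gives way to any specific instruction, and the table note is such an instruction. With one group, a total column would only duplicate the group column. If arm means regimen, as it naturally does in the comparison text, the table has one column, as Section 5 says. Reading the table note as a split by dose would give arm a different meaning there.

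**4. What is left?** Only the sentence on same drug and same dose. It can mean that subjects sharing drug and dose are combined into one group, which agrees with Section 5. It can also mean one rate per dose. The two readings coincide if one dose was given.

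Suppose instead two equal dose groups (an assumption). With no responders, the Clopper-Pearson 95% upper limit is 1 − 0.025^(1/n).

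| Display | n = 3 per dose, 6 in all | n = 6 per dose, 12 in all |
|---|---|---|
| Per dose | 1 − 0.025^(1/3) = 70.8% | 1 − 0.025^(1/6) = 45.9% |
| Pooled | 1 − 0.025^(1/6) = 45.9% | 1 − 0.025^(1/12) = 26.5% |

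With one responder among six, the lower limit is 1 − 0.975^(1/n) and the upper limit is the 97.5% quantile of Beta(2, n − 1).

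- Pooled: 1/6, 0.4% to 64.1%.
- Per dose: 1/3, 0.8% to 90.6%, and 0/3, 0% to 70.8%.

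These figures show that smaller denominators give wider intervals. They do not show that either display is wrong.

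**The case for a change.** The strongest case for a change is that the contradiction in Section 5.2 needs no assumption to see. The difference is promised outright. The phrases about whether the data warrant it, and about small samples, only choose between tests; they do not qualify the difference. A SAP written after termination should not contain an analysis its own Section 5 rules out, and that its text still speaks of small samples at the start of the trial suggests it was carried over. Stating whether doses are pooled would take one line, would need no new data, and would fix the denominator before programming. Section 5.2 also extends the rule for CBR and ORR to the transfusion summaries by treatment group, so any doubt about the unit could reach Tables 2.7 and 2.8.

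Much of this stands. The comparison text is inoperative, and the grouping sentence could be clearer. What does not stand is the step from untidy wording to a consequence for the results. No display depends on the comparison. The doubt about dose depends on a fact the SAP does not give: the title of Part 1 describes its design, not what was administered before termination, and the protocol may define treatment group. Listings 8 (exposure) and 27 (investigator-assessed responses) give the subject-level data, so a reader who prefers the other grouping can form it. Requiring pooled and per-dose rates together would add a display that the SAP's single-group instruction does not call for.

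**Conclusion.** No change to the plan is needed. The two-cohort difference and its tests are a clerical remnant that cannot be run, appear in no table, and affect no reported number. The by-arm, no-total note agrees with Section 5 once its default is read as open to override. The remaining doubt, whether the single group pools dose levels, has no effect if one dose was given. If two doses were given, the effect is on presentation: under the assumed sizes with no responders, an upper limit of 70.8% per dose against 45.9% pooled, or 45.9% against 26.5%. Either is a valid descriptive summary with its exact interval in a terminated early-phase study, where ORR and CBR are secondary endpoints for Part 1 and the streamlined tables make no comparison. An analyst would choose the grouping once the doses given are known and label the column accordingly.

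This rests on two points: that Section 5 is right about a single treatment group, and that Section 1 limits reporting to the listed displays. If a second treatment group did exist, the comparison text would need to be looked at again.
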